5. TREATMENT OF SUBJECTS

5.1 Investigational product/treatment

Intervention 1: 40 mg lycopene (i.e. 2.5 food supplement pills of Vitabiotics Ultra Lycopene 15mg, potent extract). Tablets contain 430mg Tomato Extract which provides 15mg pure Lycopene, no artificial colours or preservatives, made by Vitabiotics, UK.

Intervention 2: 250 ml of tomato soup with 20 ml olive oil. Soup will be prepared from 5 kg freshly harvested tomatoes (Harvest of Health lycopene enriched tomato), blended, and frozen down at -20 C for max 1 week. These tomatoes have been characterised previously on their lycopene content which will be determined again at Wageningen University Human Nutrition Research Unit of Wageningen University and Research.

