ABR	General Assessment and Registration form (ABR form), the application form that is required for submission to the accredited Ethics Committee; in Dutch: Algemeen Beoordelings- en Registratieformulier (ABR-formulier)
AE	Adverse Event
AR	Adverse Reaction
CA	Competent Authority
CCMO	Central Committee on Research Involving Human Subjects; in Dutch: Centrale Commissie Mensgebonden Onderzoek
CV	Curriculum Vitae
DSMB	Data Safety Monitoring Board
EU	European Union
EudraCT	European drug regulatory affairs Clinical Trials
GCP	Good Clinical Practice
GDPR	General Data Protection Regulation; in Dutch: Algemene Verordening Gegevensbescherming (AVG)
IB	Investigator's Brochure
IC	Informed Consent
IMP	Investigational Medicinal Product
IMPD	Investigational Medicinal Product Dossier
METC	Medical research ethics committee (MREC); in Dutch: medisch-ethische toetsingscommissie (METC)
(S)AE	(Serious) Adverse Event
SPC	Summary of Product Characteristics; in Dutch: officiële productinformatie IB1-tekst
Sponsor	The sponsor is the party that commissions the organisation or performance of the research, for example a pharmaceutical company, academic hospital, scientific organisation or investigator. A party that provides funding for a study but does not commission it is not regarded as the sponsor, but referred to as a subsidising party.
SUSAR	Suspected Unexpected Serious Adverse Reaction
UAVG	Dutch Act on Implementation of the General Data Protection Regulation; in Dutch: Uitvoeringswet AVG
WMO	Medical Research Involving Human Subjects Act; in Dutch: Wet Medisch-wetenschappelijk Onderzoek met Mensen

SUMMARY

Rationale: To determine the plasma lycopene concentration before and after an oral intake of lycopene in order to use this measurement as a life style compliance marker.

Objective: Primary objective: to determine if a plasma lycopene concentration can serve as a response parameter after a single dose of dietary lycopene.

Study design: Cross-over interventional pilot study.

Study population: Ten male healthy volunteers 18-75 years.

Intervention: Oral food supplement tablet 40 mg lycopene once, versus oral soup of cooked tomatoes equivalent to 40 mg lycopene content. In addition, the participants' habitual diet and actual food intake during the intervention will be measured using a food frequency questionnaire and a food diary.

Main study parameters/endpoints: Variation of plasma lycopene 1 hour before, and 1,3,6,12,24,48,72 hours after intervention.

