Plasma lycopene concentrations show variation between individuals, and within individuals. It is unknown if and how much a single dietary intervention with lycopene from lycopene-rich vegetables like tomatoes alters the plasma concentration, and therefore can be used as a compliance marker.

As the bioavailability and plasma kinetics of lycopene is known to a limited extend (see studies above), a scheme for plasma determinations is followed according to previous marker (GABA, also found in tomatoes, serving as an exemplary study design) research from the same Wageningen group, including a wash out period of at least two weeks between interventions in the cross-over design [7].

- 2) Is a tablet lycopene with equivalent lycopene content as effective as a single dose dietary intervention regarding the change of plasma lycopene concentration?

Previous studies suggest equivalence, which might be of interest for consumers/patients.

- 3) Is the prior food consumption of individuals, as measured by dietary questionnaires, related to the plasma lycopene levels before and after lycopene intervention?

If an existing individual high intake of lycopene as analysed by a validated questionnaire would result in a high standard plasma lycopene concentration, or little response on single dose lycopene consumption, the subject might exclude for further supplementary lycopene consumption and life style changes.

Intervention: We have chosen a single dose of 40 mg lycopene as an intervention based on the following. Previously, in a dose escalating study to 90 mg lycopene daily in men with Research protocol

recurrent PCa after primary treatment, no effects were seen on the level of PSA, in contradiction to two studies conducted in men with metastatic PCa [8]. Also in high doses maintained for several weeks no toxicity was observed, while lycopene plasma levels corresponded with dietary dose. For chronic use, the daily dose of 30 mg is recommended based on a large review [9].

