2. OBJECTIVES

Primary Objective:

To determine whether a plasma lycopene concentration can serve as a response parameter after a single dose of dietary lycopene.

Secondary Objectives:

1. To determine if a food supplement tablet lycopene with equivalent lycopene content compared to a single dose dietary intervention provides identical plasma lycopene concentration responses compared to the dietary intervention.
2. To determine the influence of prior food consumption, as measured by dietary questionnaires, on plasma lycopene levels before and after lycopene intervention.

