3. STUDY DESIGN

Cross-over interventional pilot study.

Ten healthy individuals (male 18-75 years) are randomly divided in two groups (A and B) of 5 individuals. One week before the dietary intervention a daily food questionnaire will be completed.

One hour before the intervention a blood sample will be taken (all blood samples 6 ml EDTA plasma tube). All individuals will be given an infusion needle for 26 hours. Samples are spun and plasma is pipetted and distributed over 1 ml Eppendorf cups for immediate freezing at -80 Celsius at the research lab.

Group A will take 40 mg lycopene (2,5 pills of food supplement Vitabiotics Ultra Lycopene 15mg, potent extract). Group B will take 250 ml of tomato soup (matching with 40 mg lycopene) with 20 ml olive oil. Blood sampling as described in all individuals from needle: 1,3,6,12,24 hours after intervention, and after 48 and 72 hours by direct venapunction. Wash out period of 3 weeks, after which the identical above procedure takes place including questionnaires, but group A and B changed (cross-over). All samples (n=160) will be frozen at -80, and transported on dry ice to Wageningen University for lycopene determination.

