8.3 Study procedures

Participants will be randomized into the study scheme AB versus BA (cross-over). One week before the intervention a food frequency questionnaire will be distributed to participants. Group A will take 40mg lycopene (2,5 pills of food supplement Vitabiotics Ultra Lycopene 15mg, potent extract). Group B will take 250 ml of tomato soup (matching with 40mg lycopene) with 20ml olive oil. Wash out period of 3 weeks, after which the identical procedure takes place including questionnaires, but group A and B changed (cross-over).

Blood draws are taken on indicated time points (before intervention, 1, 3, 6, 12, 24, 48 and 72 hours after intervention) in standard vacutainers (BD Vacutainer; Becton, Dickinson and Company). For the first blood draws (before intervention and 1-24 hours

after the intervention) all participants will be given an infusion needle for 26 hours. Blood draws after 48 and 72 hours will be done by direct venapunction. Next, the tubes are centrifuged at 3000g for 10 minutes at 4 °C (Sigma 4-16K; Sigma-zentrifugen). Plasma samples are immediately put on dry ice for rapid freezing. At the end of each test day, the plasma samples are stored at -80 °C until further analysis.

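### The tablet dose is misstated: 2.5 tablets of 15 mg give 37.5 mg, not 40 mg, while the soup is set to match 40 mg

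*Protocol*

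**What the plan says.** Three places in the protocol define the tablet intervention by tablet count, and all three equate 2.5 tablets with 40 mg:

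- Section 3: "Group A will take 40 mg lycopene (2,5 pills of food supplement Vitabiotics Ultra Lycopene 15mg, potent extract").
- Section 5.1: "Intervention 1: 40 mg lycopene (i.e. 2.5 food supplement pills of Vitabiotics Ultra Lycopene 15mg, potent extract").
- Section 8.3: "Group A will take 40mg lycopene (2,5 pills of food supplement Vitabiotics Ultra Lycopene 15mg, potent extract").

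Section 5.1 then gives the strength, "Tablets contain 430mg Tomato Extract which provides 15mg pure Lycopene", and section 6.1 repeats it.

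The comparator is set at the nominal 40 mg. The Summary describes "Oral food supplement tablet 40 mg lycopene once, versus oral soup of cooked tomatoes equivalent to 40 mg lycopene content", and section 3 says "Group B will take 250 ml of tomato soup (matching with 40 mg lycopene) with 20 ml olive oil". Section 8.3 repeats the soup target.

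The comparison of the two forms rests on equal content. Research question 2 in section 1 asks "Is a tablet lycopene with equivalent lycopene content as effective as a single dose dietary intervention", and secondary objective 1 in section 2 concerns "a food supplement tablet lycopene with equivalent lycopene content compared to a single dose dietary intervention".

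**The concern.** The tablet count multiplied by the strength does not give the stated dose. The wording in section 5.1 asserts identity, and nothing marks 40 mg as rounded. Elsewhere the authors do mark approximations: the soup content in section 1 and the tomato mass in section 6.4 are both given as approximate. Sections 6.5 and 6.6, where a dose would normally be justified and specified, are marked as not applicable, so nothing there corrects the figure.

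What is at stake is the tablet-versus-soup comparison. If the soup meets its 40 mg target, every man receives more lycopene from the soup than from the tablets. A small part of any difference between the two curves is then dose, not form of intake. Randomising the order and crossing over do not remove this, because the gap belongs to the treatment itself. A report that takes its dose from the protocol would also publish a wrong tablet dose.

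**Working it through.** **Inputs**

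- Tablets per dose: 2.5 (sections 3, 5.1, 8.3).
- Lycopene per tablet: 15 mg (sections 5.1, 6.1).
- Stated tablet dose: 40 mg (Summary, sections 3, 5.1, 8.3).
- Soup target: 40 mg (Summary, sections 3, 8.3).
- Tomato content: 8.4 mg per 100 g (section 6.1).
- Acceptable daily intake: 0.5 mg/kg, worked in section 6.4 to 40 mg for an 80 kg man.

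**Step 1: reproduce the stated dose.** Dose = tablets × strength = 2.5 × 15 = 37.5 mg. The stated 40 mg is not reproduced.

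**Step 2: look for a tablet count that gives 40 mg.**

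| Tablets | Lycopene |
|---|---|
| 2 | 30 mg |
| 2.5 | 37.5 mg |
| 40/15 = 2.67 | 40 mg |
| 3 | 45 mg |

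No whole or half tablet count gives 40 mg.

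**Step 3: size of the error.** 40 − 37.5 = 2.5 mg, and 2.5/40 = 6.25% below the stated dose.

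**Step 4: mismatch between the stated doses.** Soup target / tablet dose = 40/37.5 = 1.067, so the soup target is 6.7% higher.

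**Step 5: tomato needed for a matched soup.** For 37.5 mg: 37.5/8.4 × 100 = 446 g. For 40 mg: 40/8.4 × 100 = 476 g. Both ignore processing losses.

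**Step 6: match downwards or upwards?** At 0.5 mg/kg, 37.5 mg is the limit for a 75 kg man (37.5/0.5) and 45 mg is the limit for a 90 kg man (45/0.5). For the protocol's own 80 kg example, 37.5 mg is under the 40 mg limit and 45 mg is over it.

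**The case against.** The strongest reply accepts the arithmetic and disputes its weight.

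- **Nobody is misdosed.** Product, strength and tablet count are explicit and consistent, so each man swallows the same 2.5 tablets whichever total is printed. This is correct, and it is why the point does not threaten conduct or safety.
- **No calculation depends on the dose.** Section 10 plans no statistical calculations, and no margin, test or power figure uses the dose. As an illustration, assume that the response scales linearly from the single-dose figure in section 1 (15 mg raised a base of about 400 nmol/l by 40 nmol/l). Then 37.5 mg gives 40 × 37.5/15 = 100 nmol/l (25%), and 40 mg gives 40 × 40/15 = 107 nmol/l (27%). Both are well above the 10% rise in section 4.4. This also stands, and it limits the effect on the main endpoint in section 8.1.1.
- **The delivered soup dose is not known.** Section 5.1 gives 5 kg of tomatoes but no number of portions. If 5 kg made ten portions, each would hold 500 × 8.4/100 = 42 mg before losses, so the real soup dose could lie above or below 37.5 mg. The direction of any real imbalance therefore cannot be fixed from the protocol. But the renewed lycopene determination in section 5.1 concerns the tomatoes and leaves the tablet figure wrong. A soup portioned accurately to 40 mg would build in the mismatch.
- **Olive oil matters more.** Oil is stated only with the soup, although section 1 says that fat promotes uptake. It is probably a larger source of difference than 2.5 mg, but it does not make the dose figure right.
- **The intake argument for 37.5 mg over 45 mg is partial.** Men under 75 kg would exceed 0.5 mg/kg even at 37.5 mg, and section 1 reports no toxicity at higher sustained doses. The argument supports a preference for rounding down and shows no hazard at either dose.

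**Conclusion.** The point holds, and it should be fixed. By the protocol's own figures the tablet dose is 37.5 mg, which is 6.25% below the 40 mg stated in the Summary and in sections 3, 5.1 and 8.3. The stated soup target is 1.07 times the tablet dose, which contradicts the equal-content premise of research question 2 and secondary objective 1.

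The misstatement rests only on the printed tablet count and strength. The inequality between arms is one of stated doses; it becomes one of delivered doses only to the extent that the soup meets its target. The consequence is modest, since the comparison is descriptive in ten men and each man's rise from T0 is hardly touched. It does not call the trial's validity into question.

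**What to change.** 1. **Tablets.** In the Summary and sections 3, 5.1 and 8.3, state the dose as 37.5 mg (2.5 tablets × 15 mg).
2. **Soup.** In the Summary and sections 3 and 8.3, set the target to 37.5 mg, which is about 446 g of tomato at 8.4 mg per 100 g.
3. **Rationale.** Align the 40 mg single-dose wording for this study in sections 1 and 4.4.
4. **Reporting.** Give the milligrams of lycopene in each arm beside the descriptive comparison.

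Matching downwards is preferable to three tablets with a 45 mg soup, because 45 mg would exceed the daily maximum that section 6.4 derives for an 80 kg man.

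One clarification would help but is not part of the error: state the tomato mass per portion and any reduction step, and use the determination already planned in section 5.1 to confirm the portion. Assuming 1 g/ml, 250 ml of unreduced blend would hold 250 × 8.4/100 = 21 mg. The generic soup figure in section 1 (33 mg per 200 g) implies 33/200 × 250 = 41 mg per 250 g.

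The cost is protocol wording and soup portioning, with no assay beyond the one planned. The single dose becomes 6.25% lower than the 40 mg in the rationale, which for the tablets is what 2.5 tablets deliver in any case.

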5.2 Use of co-intervention

Subjects are allowed to continue their normal diet without alterations.

5.3 Escape medication

Not applicable.

6. INVESTIGATIONAL PRODUCT

6.1 Name and description of investigational product(s)

Food supplement Vitabiotics Ultra Lycopene 15mg, potent extract. Tablets contain 430mg Tomato Extract which provides 15mg pure Lycopene, no artificial colours or preservatives, made by Vitabiotics, UK.

Tomatoes are a source of bioactive phytochemicals and are widely consumed. The phytochemical pattern of tomato products can be refined by choosing breeds with naturally higher nutrient levels that require more intense horticultural techniques and food processing [13]. Producing high-nutrient tomatoes is achieved through classic and conventional breeding techniques, done by professional vegetable breeding companies, as indicated in European Union Law. This process does not include genetic modification processes. In this study the Harvest of Health (Proudesse) tomato will be used. Per 100g this tomato contains 8,4mg lycopene, which is three times higher as 'normal' supermarket tomatoes. Unique characteristics of the Proudesse tomato are its preservability, shape, high concentration of lycopene and its taste.

Per subject 250 ml of tomato soup with 20 ml olive oil will be prepared from freshly harvested Harvest of Health lycopene enriched tomatoes, blended, and frozen down at -20 °C for max one week.

6.2 Summary of findings from non-clinical studies

Food supplement Vitabiotics Ultra Lycopene 15mg, potent extract: we are not aware of any performed non-clinical studies.

Harvest of health tomato: studies have been conducted measuring the nutrient levels over time, confirming that the Harvest of Health tomato contains almost 3x higher lycopene levels as compared to the normal supermarket tomato. This was recently confirmed by measurements performed by the Wageningen University.

6.3 Summary of findings from clinical studies

Food supplement Vitabiotics Ultra Lycopene, 15mg, potent extract: we are not aware of any performed clinical studies.

Harvest of Health tomato: to the knowledge of the research group, no clinical studies have been done with the Harvest of Health (Proudesse) tomato.

6.4 Summary of known and potential risks and benefits

Food supplement Vitabiotics Ultra Lycopene, 15mg, potent extract: according to the manufacturers' frequently asked questions page 'Ultra Lycopene has no known side-effects when taken as directed' (<https://www.vitabiotics.com/products/ultra-lycopene-tablets>).

Harvest of Health tomato: the Harvest of Health tomato contains 8,4mg lycopene per 100gr. The acceptable daily intake of lycopene is 0,5 mg/kg bodyweight. For an average male participant weighing 80kg this would result in consuming a maximum of 40mg lycopene per day, converting into a daily uptake of \pm 500gr of tomatoes. It is not likely that participants will eat more than 500gr of tomatoes per day and therefore the risk of consuming too much lycopene is low.

6.5 Description and justification of route of administration and dosage

Not applicable.

6.6 Dosages, dosage modifications and method of administration

Not applicable.

6.7 Preparation and labelling of Investigational Medicinal Product

Not applicable.

6.8 Drug accountability

The food supplement Vitabiotics Ultra Lycopene 15mg, potent extract supplement has been bought in store and stored dry and at room temperature.

Blended tomato fluids (soup) are frozen till consumption, and heated at normal soup temperature circa 60-80 degrees Celsius.

7. NON-INVESTIGATIONAL PRODUCT**7.1 Name and description of non-investigational product(s)**

Not applicable.

7.2 Summary of findings from non-clinical studies

Not applicable.

7.3 Summary of findings from clinical studies

Not applicable.

7.4 Summary of known and potential risks and benefits

Not applicable.

7.5 Description and justification of route of administration and dosage

Not applicable.

7.6 Dosages, dosage modifications and method of administration

Not applicable.

7.7 Preparation and labelling of Non Investigational Medicinal Product

Not applicable.

7.8 Drug accountability

Not applicable.

8. METHODS

8.1 Study parameters/endpoints

8.1.1 Main study parameter/endpoint

Raise of plasma lycopene concentration in absolute (ng/ml) and relative (percentage of T0-value) after single lycopene intervention.

8.1.2 Secondary study parameters/endpoints

1. Optimal time point of lycopene concentration response after single dietary intervention (hours, days).
2. Influence of prior food consumption on plasma lycopene levels before and after lycopene interventions, as measured by dietary questionnaires.

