While the generally accepted opinion is that diets high in antioxidants are beneficial for suppressing and prevention of all cancers, and that they promote the overall health status of individuals, it may be difficult to change a life style that incorporates a healthy diet. Therefore in this study, we are searching for a parameter in body fluids that reflects the intake of healthy diet, and as such may motivate and sustain its continuous use (compliance marker). In case of prostate cancer we address lycopene as our target for reasons described above. Ideally, our lycopene related marker should reflect the short-term uptake of lycopene, and be based on a single dose consumption, in order to act as a direct feed-back to the consumers dietary action. Current methods of determination (see further) do not yet live up to point-of-care applications. There is, however, evidence that single dose consumption is reflected in the lycopene plasma concentration. In a trial in Italian consumers on lycopene kinetics on single dose consumption [5], a significant increase of plasma lycopene concentration of 40

nmol/l was observed above an individual base level (around 400 nmol/l), with a max concentration at 12 hours, and a normalisation after 48 hours after consumption of 15 mg of lycopene. Also a biomarker reflecting the adequate lycopene consumption of a medium long term (e.g. one week consumption) might provide a valuable asset for consumers. In a trial in Swiss male consumers on an 8-day intervention of 20 mg after lycopene depletion, the individual lycopene plasma concentration topped to a steady state of 1000 to 1500 nmol/l, while two weeks after the intervention (so during lycopene depletion) a plateau phase was obtained on a plasma concentration of 400-500 nmol/l [4], likely due to the release of lycopene from liver resources. We conclude that for consumer reasons the choice for a point-of-care testing of single dose lycopene is feasible, but restricted by current technology, and that feed-back on medium long term lycopene consumption is also feasible, as it is well reflected in plasma lycopene concentrations.

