Study design: We have chosen lycopene as it is related to PCa growth, it can be used as a dietary intervention, and it is measurable reproducibly in food and in body fluids. Here we study the lycopene plasma concentration dynamics after a single dose consumption in volunteers in a Dutch setting (which differs from the geographic and environmental setting and life-style in the above mentioned studies). This is to obtain the necessary information on technology, logistics, and food products needed to conduct the follow-up study (METC 2017-389) in cancer patients. Once we have proven that a measurable response can be obtained in healthy volunteers in a Dutch population, that the assay is available and robust, and in line with food consumption as evaluated by validated food questionnaires, we will incorporate that parameter (lycopene) in the current randomised study for men with PCa and undergoing treatment or have undergone treatment in the past in which three dietary interventions are given and compliance to the intervention is currently measured by food intake questionnaires (METC 2017-389).

Here we test plasma lycopene as a candidate compliance marker for that purpose. This is based on the assumption that in Dutch participants the plasma level of lycopene might be comparable to the Swiss population literature, that a single dose response to 40 mg lycopene in combination with oil will provide a measurable response of plus 10 % in individuals, and that a concentration between 1000-1500 nmol/l is appreciated by patients and caregivers as the optimal lycopene plasma concentration to be accomplished long term (1-3 months).

Dietary interventions should always be analysed against the background of the normal individual diet. Therefore, to evaluate the lycopene intervention and related marker, it is

crucial to take the participant's habitual diet, as well as actual food intake during the intervention into account [6].

Research questions:

- 1) Can a plasma lycopene concentration serve as a response parameter after a single dose of dietary lycopene.

We will measure plasma carotenoid concentrations (including lycopene) in response to a single dose dietary intervention with lycopene-rich food or a lycopene tablet in a cross-over study design.

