4.4 Sample size calculation

Observational study obtaining individual lycopene concentration curves in plasma. It is anticipated that a measurable lycopene response will be seen in all participants. Based on the literature described in the introduction section it is hypothesized that in Dutch participants the plasma level of lycopene might be comparable to the Swiss population, that a single dose response to 40mg lycopene in combination with oil will provide a measurable response of plus 10% in all individuals. Therefore a sample size of two times five participants (10 participants in total) has been chosen.

Our pilot still needs to obtain an impression that responses are observed in all individuals, and to confirm that our HPLC-assay is an adequate technique. We will express that in

percentages of the group, such as: 'In xx percent the lycopene concentration increased more than 10% of the T=0 within 48 hours after intervention A'.

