10.2 Secondary study parameter(s)

Lycopene plasma concentration curves over time will be depicted in tables and in graphs in absolute and relative (compared to T0) amounts. Trends in changes over time will be interpreted, if needed based on background information on confounding parameters.

There are no statistical calculations planned.

FFQ and food diary data will be reported descriptively.

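### The optimal time point is picked from seven sampling times in ten men, is not defined, and will be reported with no measure of certainty

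*Protocol*

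**What the plan says.** - Section 8.1.2, secondary endpoint 1: "Optimal time point of lycopene concentration response after single dietary intervention (hours, days". It does not say whether this is the peak of the group mean, each man's own peak or the time with most responders. It also does not say whether it is judged on absolute or relative change, or for the soup, the tablet or both.
- Summary, main study parameters: "Variation of plasma lycopene 1 hour before, and 1,3,6,12,24,48,72 hours after intervention". That gives one baseline and seven candidate times.
- Section 4.4: "Therefore a sample size of two times five participants (10 participants in total) has been chosen". In a cross-over this gives ten curves per product and twenty in all.
- Section 10.2 plans tables and graphs of the curves, then: "Trends in changes over time will be interpreted, if needed based on background information on confounding parameters". It closes with: "There are no statistical calculations planned". The same sentence stands in the opening of section 10 and in 10.1 and 10.3. It is a positive statement of the plan, not a detail left open for a statistical analysis plan.
- Section 1, on the purpose of the pilot: "This is to obtain the necessary information on technology, logistics, and food products needed to conduct the follow-up study".

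**The concern.** The highest of seven noisy means is partly signal and partly luck. With ten men and an expected rise of about a tenth of baseline, the observed maximum can easily fall beside the true one. Without an interval or a stability check, a reader cannot tell a clear peak from a flat stretch of curve on which one time happened to come out highest.

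Because *optimal* is undefined, the group-mean peak, the typical individual peak and the time with most responders could each be reported under the same name after the data are seen. What is at stake is how far this one secondary result can be trusted. The primary objective is not affected.

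**Working it through.** **Nothing to reproduce.** The ten participants come with no precision target or SD. The sample count is consistent: 10 men × 2 periods × 8 samples = 160, as section 3 states.

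**Inputs from the protocol.** Section 1 cites a single-dose study with "a significant increase of plasma lycopene concentration of 40" nmol/l "above an individual base level (around 400 nmol/l), with a max concentration at 12 hours, and a normalisation after 48 hours". So the signal is 40/400 = 10%, peaking at 12 h. Section 4.4 also expects +10%. Section 1 acknowledges within-person variation but gives no figure.

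**Assumed.** Per-sample within-man CV; the heights at 6 and 24 h; between-man SD of the response equal to 40% of its mean, acting as one factor per man across all times; independent errors.

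**Check 1: how often is the true best time picked?** The measured value for man *i* at time *t* is (1 + m_t·f_i)(1 + CV·e_it), with f_i of mean 1 and SD 0.4. It is divided by a T0 value with the same CV. The pick is the time with the highest mean relative change over ten men, one product, 20,000 trials per cell. Mean rises at 1, 3, 6, 12, 24, 48, 72 h are: broad 1, 4, 8, 10, 8, 2, 0%; sharper, the same with 6% at 6 and 24 h; doubled, twice the broad curve.

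| Curve | Result | CV 3% | CV 5% | CV 10% |
|---|---|---|---|---|
| Broad | pick is 12 h | 85% | 68% | 49% |
| | pick is 6, 12 or 24 h | 100% | 99.8% | 95% |
| | true rise at pick (best 10%) | 9.7% | 9.3% | 8.7% |
| Sharper | pick is 12 h | 99% | 91% | 64–65% |
| | pick is 6, 12 or 24 h | 100% | 99.5% | 92% |
| | true rise at pick (best 10%) | 10.0% | 9.6% | 8.3% |
| Doubled | pick is 12 h | 99% | 88% | 65% |

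If each man's deviation is instead drawn separately at each time, the broad-curve row falls to 72, 62 and 49%.

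**Check 2: a different error model.** Here the errors are additive with SD = CV × 400 nmol/l, and there is no between-man spread. For a broad peak (+30, +40, +35 nmol/l at 6, 12, 24 h) and ten curves, the wrong time is picked in 34, 50 and 58% of runs at CV 5, 10 and 15%. For a sharp peak (+20, +40, +20) it is 2, 23 and 41%. Treating both products as twenty independent curves lowers the broad-peak figures to 24, 43 and 51%.

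**Check 3: what an interval would show.** The 95% half-width for the mean difference between two times in the same ten men is t(0.975; 9) × 400·CV·√2/√10, with t = 2.262:
- CV 5%: 2.262 × 20 × 0.447 = 20 nmol/l
- CV 10%: 2.262 × 40 × 0.447 = 40 nmol/l
- CV 15%: 2.262 × 60 × 0.447 = 61 nmol/l

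The assumed gap between 12 h and a neighbour is only 5 to 20 nmol/l. At these CVs neighbouring times would usually not be separated.

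**The case against.** This is a descriptive pilot with no decision rule on this endpoint. The curves will be tabulated and plotted, so readers will see the neighbouring times. The wording in 8.1.2 allows an answer as coarse as days, and nothing forbids reporting a window. A wrong pick is usually next door. On the broad curve the true rise at the picked time averages 8.7 to 9.7% against 10%. The 10% peak is also the rise cited after 15 mg, whereas this trial gives 40 mg, so the signal may be larger and the pick firmer. All of this stands and keeps the point small. It does not supply a definition or a measure of certainty, and plots of means alone do not show how stable the maximum is.

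A reader might infer two stronger harms, which the documents do not support:
- **That a chance hour will be carried into the follow-up study.** Sections 1 and 12.6 say that the pilot informs that study, and section 1 says that lycopene would be added as a parameter. Neither says that a sampling hour is transferred.
- **That the response quoted at the chosen time will be overstated.** The summary given as an example in 4.4 is the share of men rising more than 10% over T0 at any time within 48 h. No response at the chosen time is planned. If one were quoted, the optimism would depend on the selection rule. In the broad scenario the share of men above +10% would be overstated by about 7, 10 and 14 points if the time is chosen by that same share, but by about 3, 5 and 8 points if it is chosen by the highest mean.

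**Conclusion.** The point holds in a limited form. A named secondary endpoint is undefined, and the plan expressly excludes any calculation that would show its certainty. Under the assumptions above, the observed maximum misses the true best time in anything from about 1% of trials (sharper or doubled curve, CV 3%) to about half (broad curve, CV 10%). With additive error and CV 15% it reaches 58%. The protocol gives no CV and no curve shape, so its own figures cannot place the trial within that range.

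The consequence is modest: a miss usually lands on 6 or 24 h. It costs little if the peak is broad and more if it is sharp (6% against 10% in the sharper curve). This is a worthwhile improvement, not a flaw that threatens the study. It shows neither that the follow-up study will be mis-timed nor that a planned response figure is biased.

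**What to change.** - **Section 8.1.2:** define *optimal*, for example as the time of the highest mean change from T0, separately for each product, and state whether the change is absolute or relative.
- **Section 10.2:** for this endpoint, replace the statement that nothing will be calculated with (a) each man's own peak time; (b) the mean change with a 95% interval at each time; (c) the frequency with which each time is chosen when the ten men are resampled by bootstrap, keeping each man's whole curve together.
- **Reporting:** where neighbouring times are not separated, give a window (for example 6–24 h) instead of one hour, and label the result exploratory.
- **Only if a response is quoted at the chosen time:** estimate it from men left out of the choice, or state that it is optimistic.

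The cost is a few lines of analysis on data already collected, with no extra samples, visits or participants. The answer may be a window instead of a single hour.
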